6.0 Table 1 - Schedule of Activities

		NTRP101-203										
Week	Screening	0	1	2	3	5	7	9	11	13	15/ET	
Day (±2 days)	(Days -28 to -2) ^d	0	7	14	21	35	49	63	77	91	105	
Dose	Rand	1	2		3	4	5	6	7			
Informed Consent	X											
Medical history	X											
Demographics	X											
Rosen-modified Hachinski Scale	X											
SIB	X ^a					X*		X*		X	X	
MMSE-2	X					X*		X*		X	X	
ADCS-ADL-Sev ^b	X					X*		X*		X	X	
NPI ^b	X					X*		X*		X		
CGI-I						X*		X*		X		
CSSRS	X			X			X*			X		
Labs ^{^^}	X			X			X*			X		
ECG	X (x3)			X			X			X		
PE	X						X* ⁺			X		
Vitals	X	X ^c	X ^c	X	X ^c	X ^c	X ^c	X ^c	X ^c	X ^c	X	X
Randomization		X ^a										
Confirm Eligibility	X [◊]	X										
Study Drug Dosing		X	X		X	X	X	X	X			
Adverse Events	X	X	X	X	X	X	X	X	X	X	X	
Con meds	X	X	X	X	X	X	X	X	X	X	X	

^aBaseline SIB administered during screening must be done within 3 weeks of the first dose of study drug. If the screening period exceeds 3 weeks, the SIB should be repeated on the day of first dose, prior to dosing; * before dose; ^^Labs: CBC including differential, coagulation, clinical chemistry, TSH at screening (B12, T-3 and T-4 if TSH abnormal), CPK at screening and event of myalgia, βhCG if indicated, HbA1C if clinically indicated; [◊] CT scan if necessary per inclusion criterion #6; ⁺ abbreviated physical examination; ^a Randomization after initial screening procedures indicate eligibility; ^b The ADCS-ADL-Sev and NPI may be administered via telephone at the discretion of the investigator, within the allowed time window for the scheduled visit; ^c Vital signs prior to infusion, then at 30, 60 and 90 minutes from start of the infusion (+/- 5min). ^dThe visit window of ±2 Days does not apply to the Screening and Randomization period which is a maximum of 28 days.

6.1 Assessments

Every effort should be made to ensure that protocol-required tests and procedures are completed as described. However, it is anticipated that from time to time there may be circumstances outside the control of the PI that may make it unfeasible to perform a test. In these cases, the PI must take all steps necessary to ensure the safety and well-being of the subject. When a protocol required test cannot be performed, the PI will document the reason for the missed test and any corrective and preventative actions which were taken to ensure that the required processes are adhered to as soon as possible. The study team must be informed of these incidents in a timely manner.

6.1.1 Safety

Overall safety and tolerability will be assessed by the incidence of treatment emergent AEs and SAEs and by evaluations of change from baseline in physical examination, vital signs, 12-lead ECG, the C-SSRS, clinical chemistry, hematology, and coagulation lab tests.

6.1.1.1 Laboratory

Blood samples will be obtained for routine laboratory tests, including hematology, chemistry, coagulation and β hCG if indicated as outlined in the Schedule of Activities (Table 2).

Hematology tests will include CBC with differential, platelet count and coagulation (prothrombin time (PT) and partial prothrombin Time (PTT)) studies.

Clinical chemistry tests will include sodium, potassium, chloride, bicarbonate, blood urea nitrogen (BUN), creatinine, estimated creatinine CL, glucose, calcium, CO₂, total protein, albumin, ALP, ALT, AST, gamma glutamyl transferase (GGT) lactate dehydrogenase (LDH), uric acid and bilirubin. A serum creatine phosphokinase (CPK) will be done at screening and in the event of myalgia. A TSH will be done at screening, and B12, T-3 and T-4 will be done if TSH result is abnormal.

Samples will be sent to a central lab for testing. Refer to the Laboratory Manual for detailed instructions.

6.1.1.2 Physical Examination

All physical examinations must be performed by the PI or qualified designee (physician, physician's assistant, or nurse practitioner). The complete physical examination conducted during the screening period and at designated subsequent time points should include, but is not limited to the following:

- General appearance
- Weight
- Height (screening only)
- Ears

- Eyes
- Nose
- Throat
- Neck
- Respiratory system
- Cardiovascular system
- Abdomen
- Musculoskeletal /Neurologic
- Extremities
- Skin
- Lymph nodes

An abbreviated PE will include but is not limited to the following:

- General appearance
- Weight
- Respiratory system
- Cardiovascular system
- Abdomen

Examination of other systems as needed to explore reports of AEs should be conducted as needed by the PI. Any clinically significant physical findings that were not present on the initial physical examination will be considered AEs and documented on the AE eCRF as well as in the subject's source documentation and on the physical examination eCRFs.

6.1.1.3 Vital Sign Measurements

Single supine blood pressure and pulse rate will be measured at Screening and at other visits as specified in the Schedule of Activities.

6.1.1.4 Electrocardiogram

An average of triplicate 12-lead ECGs will be collected at screening. The triplicate ECG measurements should be obtained approximately 2-4 minutes apart. Single 12-lead ECGs will be collected at time points specified in the Schedule of Activities.

6.1.1.5 Columbia Suicide Severity Rating Scale

The C-SSRS is an interview-based rating scale to systematically assess suicidal ideation and suicidal behavior. The scale should be administered by an individual with appropriate clinical training, who has also taken the specific rater training for the scale, which will be provided by an agent of the Sponsor prior to the study start. If at any visit from baseline on, there are "YES" answers on items 4, 5 or on any behavioral question of the C-SSRS, a risk assessment should be done by a qualified clinician to determine whether it is safe for the subject to continue to participate in the study. A suicidality narrative should be constructed for subjects who have

undergone any post-baseline risk assessment, using information from the C-SSRS, and available information from the NPI, prior screening and baseline information, the clinician assessment and the narrative guide. Subjects who answer “YES” on items 4, 5 or on any behavioral question of the C-SSRS on more than one occasion during a study should be discontinued from the study. Suicidality AEs or other clinical observations may, based on the judgment of the PI, also trigger a risk assessment and a narrative. When there is a positive response to any question on the C-SSRS, the PI should determine whether an AE has occurred.

6.1.2 Efficacy / Psychometric Assessments

All raters for the efficacy assessments need to be trained and qualified on the administration of the scales. A qualified rater is required for the administration of the SIB, NPI and MMSE-2.

The same qualified rater should perform a given Efficacy/Psychometric Assessment at approximately the same time of day for a given subject throughout the study. All changes in raters for a given assessments must be noted in the subject’s source documents. The caregiver designated to provide assessments (ADCS-ADL-Sev and NPI) at the start of the study should be the same individual throughout the study. Should a change be necessary during the course of the study, the reason for the change and the first corresponding visit must be noted in the subject’s source document.

All psychometric tests performed on study subjects on the same day should be administered in the following order: SIB followed by MMSE-2, except at the screening visit as described in Section 6.2.1. If the MMSE-2 score obtained at screening does not fall within the 4-15 range for inclusion, no further screening tests should be performed. Efficacy tests at subsequent visits should be administered prior to dosing.

6.1.2.1 Rosen-Modified Hachinski Scale

The Rosen-Modified Hachinski Scale will be evaluated at screening to differentiate Alzheimer’s type dementia from multi-infarct dementia. The 8-item scale results in a score of 0-12; and a score of 5 or above is exclusionary for the study.

6.1.2.2 Severe Impairment Battery

The SIB is used to assess cognition in subjects with moderate and severe AD. It is divided into nine subscales that include attention, language, orientation, memory, praxis, visuospatial ability, construction, social skills, orienting head to name. Non-verbal responses are allowed, thus decreasing the need for language output. Forty questions are included with a point score range of 0-100. Lower scores indicate greater cognitive impairment.

6.1.2.3 Mini Mental State Examination, 2nd Edition

The Standard version of the MMSE-2, with two alternate forms, will be used. This version has the structure and scoring of the original 30-item MMSE-2 and scores are comparable. The MMSE-2 is a brief, widely used test for assessing overall cognitive state. The MMSE-2 measures selected aspects of cognition such as memory, orientation, attention, language, and praxis on a scale of 0-30. Lower scores indicate greater cognitive impairment.

6.1.2.4 Alzheimer's Disease Cooperative Study Activities of Daily Living Inventory – Severe Impairment Version

The ADCS-ADL-Sev is a 19-item functional assessment of the performance of activities of daily living for subjects with moderate to severe Alzheimer's disease. Informants are queried via a structured interview format as to whether subjects attempted each item in the inventory during the previous 4 weeks, as well as their level of performance. Each item is rated from the highest level of independent performance to complete loss. Total score ranges from 0-54 with lower scores indicating greater functional impairment. The ADCS-ADL-Sev may be administered via telephone at the discretion of the PI, within the allowed time window for the scheduled visit.

6.1.2.5 Neuropsychiatric Inventory

The NPI is a caregiver interview-based rating scale assessing 10 behavioral disturbances occurring in dementia subjects. The NPI may be administered via telephone at the discretion of the investigator, within the allowed time window for the scheduled visit. Items are scored for both frequency and severity. Total scores range from 0-120 with higher scores indicating greater behavioral disturbances. For each item, the associated caregiver distress is also assessed.

6.1.2.6 Clinical Global Impression of Improvement Scale

The CGI-I is used to assess global change in the subject's condition compared to baseline before treatment. The same Clinician must complete the CGI-I scale at each scheduled visit. This is a seven-point scale ranging from (1) very much improved to (7) very much worse.

6.2 Visit Procedures

6.2.1 Screening and Randomization (Days -28 to -2)

In order to avoid unnecessary screen failures, a prescreening telephone call to rule out clearly exclusionary conditions is advised prior to scheduling a screening visit. Informed Consent must be obtained before any study related procedures are performed. Screening procedures and randomization will take place within an approximate 4-week period prior to first dose administration (Days -28 to -2).

Subjects who are screen-failed (e.g. due to clinically significant laboratory abnormality or an active medical condition) may be re-screened if their medical condition stabilizes or improves as assessed by the PI. Subject who are screen-failed due to MMSE score may be rescreened in 3 months.

The Medical Monitor should be consulted prior to re-screening. Subjects who are Screen Failures may be rescreened only once.

The following procedures should be performed first to avoid unnecessary procedures for ineligible subjects:

- Collection of subject demographic data
- Review of concomitant medications

- Review of medical history
- Assessment of neuroimaging (CT or MRI performed within 2 years of screening)
- Evaluate Rosen-Modified Hachinski Scale
- Evaluate MMSE-2

After confirming that these parameters satisfy eligibility criteria, the remaining screening procedures should be performed;

- SIB. The SIB should be done within 3 weeks before the first study drug dose. If the screening period exceeds 3 weeks, the SIB should be repeated on the day of the first dose, prior to dosing. The repeat SIB score obtained closest to the day of dosing should be recorded in the eCRF as an unscheduled visit.
- NPI
- ADSC-ADL-SIV
- Columbia Suicide Severity Rating Scale (C-SSRS)
- Blood samples for routine safety including hematology, PT, PTT, INR and serum-chemistry, CPK, TSH (B12, T-3 and T-4 if indicated), and β -hCG, if indicated
- 12-lead ECG (x3)
- Complete physical examination
- Vital signs
- AEs and concomitant medications

If changes in the subject's health or mental status occur during the screening and randomization period, including changes in medication affecting the mental status, the Medical Monitor should be notified. The Medical Monitor will advise the PI regarding any assessments that should be repeated to ensure eligibility requirements are met.

Sites will not be able to randomize subjects before confirmation that eligibility criteria have been met per the review of the Rosen-Modified Hachinski Scale, MMSE-2, CSSRS, and other eligibility criteria by the Worldwide Clinical Trials' Clinical Assessment Technologies (CAT) group and Medical Monitor (MM).

6.2.2 Week 0 (Day 0 Dose 1)

If the subject has had no intervening medical issues or changes in medications between the date of randomization and Week 0, dosing may proceed as scheduled.

A final assessment of the inclusion/exclusion criteria, including any changes in medications or health status will be done before dosing to confirm the subject's eligibility.

The following procedures will be done on Day 0:

- *Dosing by IV infusion* will be done according to the procedures outlined in Section 5.7.

- Vital signs prior to infusion, then at 30(\pm 5), 60(\pm 5) and 90(\pm 5) minutes from start of the infusion
- AEs and concomitant medications

6.2.3 Week 1 (Day 7 \pm 2 days Dose 2)

One week after the first dose of study drug, subjects will return for a second infusion. The following procedures will be performed:

- Vital signs prior to infusion, then at 30(\pm 5), 60(\pm 5) and 90(\pm 5) minutes from start of the infusion
- *Dosing by IV infusion*
- AEs and concomitant medications

6.2.4 Week 2 (Day 14 \pm 2 days/ No dose)

- C-SSRS
- Blood samples for routine safety
- 12-lead ECG
- Vital signs
- Adverse events and concomitant medications

6.2.5 Week3 (Day 21 \pm 2 days/ Dose 3)

- Vital signs prior to infusion, then at 30(\pm 5), 60(\pm 5) and 90(\pm 5) minutes from start of the infusion
- *Dosing by IV infusion*
- Adverse events and concomitant medications

6.2.6 Week 5 (Day 35 \pm 2 days/ Dose 4)

- Prior to dosing:
 - SIB
 - MMSE-2
 - ADCS-ADL-Sev
 - NPI
 - CGI-I

- Vital signs prior to infusion, then at 30(\pm 5), 60(\pm 5) and 90(\pm 5) minutes from start of the infusion
- *Dosing by IV infusion*
- AEs and concomitant medications

6.2.7 Week 7 (Day 49 \pm 2 days/ Dose 5)

- Prior to dosing:
 - C-SSRS
 - Blood samples for routine safety
 - 12-lead ECG
 - Abbreviated Physical exam
- Vital signs prior to infusion, then at 30(\pm 5), 60(\pm 5) and 90(\pm 5) minutes from start of the infusion
- *Dosing by IV infusion*
- AEs and concomitant medications

6.2.8 Week 9 (Day 63 \pm 2 days/ Dose 6)

- Prior to dosing:
 - SIB
 - MMSE-2
 - ADCS-ADL-Sev
 - NPI
 - CGI-I
- Vital signs prior to infusion, then at 30(\pm 5), 60(\pm 5) and 90(\pm 5) minutes from start of the infusion
- *Dosing by IV infusion*
- AEs and concomitant medications

6.2.9 Week 11 (Day 77 \pm 2 days/ Dose 7)

- Vital signs prior to infusion, then at 30(\pm 5), 60(\pm 5) and 90(\pm 5) minutes from start of the infusion
- *Dosing by IV infusion*

- Adverse events and concomitant medications

6.2.10 Week 13 (Day 91 ±2 days)

At Week 13, subjects will undergo efficacy assessments as well as routine safety assessments. The following will be performed:

- SIB
- MMSE-2
- ADCS-ADL-Sev
- NPI
- CGI-I
- CSSRS
- Blood samples for routine safety
- 12-lead ECG
- PE
- Vital signs
- AEs
- Concomitant medications

6.2.11 Week 15 or End of Treatment Follow-up Visit

For subjects who have completed the study, a follow-up visit will take place at Week 15, 30 days after the last dose of study drug. Subjects who have withdrawn from the study will have a follow-up visit 30 days after the last dose of study drug. The following will be performed:

- SIB
- MMSE-2
- ADCS-ADL-Sev
- Vitals
- AEs and concomitant medications

6.3 Concomitant Medications

During the screening visit, the Caregiver will provide a history of prior medication use during the past 6 months and provide a list of currently used medications. All concomitant medications used should be recorded on the eCRF and in the source documents using the generic name for the drug. Assessment of concomitant medications will take place at each study visit. Any changes to chronic medications should be noted as well as new and discontinued medications.

Subjects taking allowed antidepressant medications may be enrolled in the study (see Appendix 1). The dose and dose regimen for these medications should be stabilized for at least 30 days prior to enrollment in the study. Every effort should be made to keep the dose and dose regimen of antidepressant medications stable throughout the study.

6.3.1 Medications for AD

Subjects taking FDA approved medications for the treatment of AD, **with the exception of memantine or any drug containing memantine**, may be enrolled in the study. The subject must be on a stable dose of permitted medications for at least 3 months prior to entry into the study and dose must not change during the study. Subjects may not initiate additional drugs for treatment of AD during the study other than the study drug.

6.3.2 Concomitant Medications for Management of Myalgia

Non-steroidal anti-inflammatory drugs such as ibuprofen and naproxen sodium are permitted. Use of acetaminophen as an analgesic is contraindicated as it has the ability to inhibit PKC activation.

6.3.3 Prohibited Medications

Memantine is prohibited. Subjects previously treated with memantine must stop treatment at least 30 days prior to initiation of study drug treatment. Treatment with other NMDA receptor antagonists such as but not limited to dextromethorphan (a cough suppressant), ketamine, phencyclidine (PCP), methoxetamine (MXE), nitrous oxide (N₂O) and the following synthetic opioids: pentidine, levorphanol, methadone, dextropropoxyphene, tramadol, and ketobemidone is prohibited and a 30-day washout period is required prior to initiation of study drug treatment.

High dose Vitamin E (> 400 IU / day), Valproic Acid and divalproex sodium are prohibited.

If the PI determines that initiation of any of the prohibited medications is required to ensure the subject's safety, the medication may be initiated with the notification of the Medical Monitor and proper documentation of a protocol deviation. Other restricted concomitant medications are listed in Appendix 1.

7 ADVERSE EVENTS AND OTHER SAFETY EVALUATIONS

7.0 Definition of Adverse Events

An AE is any untoward medical occurrence associated with the use of a drug in humans, whether or not considered drug related. An AE (also referred to as an adverse experience) can be any unfavorable and unintended sign (e.g., clinically significant abnormal laboratory finding), symptom, or disease temporally associated with the use of a drug, without any judgment about causality.

The PI is responsible for obtaining information about all medical emergencies during the clinical study. The PI's contact information will be located in the body of the informed consent form (ICF) and subjects/caregivers will be encouraged to contact the PI or clinical site personnel during any clinical study-related emergency.

All adverse events spontaneously reported by the subject and/or caregiver in response to an open question or revealed by observation will be recorded during the study regardless of relationship to the study drug. All AEs will be monitored and recorded for the progress of the event until it resolves or reaches a clinically stable outcome. Adverse events that are not resolved at the time of database lock will be recorded as ongoing.

The AE and SAE reporting period starts from the time of consent to the last study visit.

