4.4.1 Inclusion Criteria

1. Written informed consent from caregiver and subject (if possible) or legally acceptable representative if different from caregiver
2. Male and female subjects 55-85 years of age inclusive
3. Cognitive deficit present for at least 2 years that meet the diagnostic criteria for probable Alzheimer's dementia.¹⁶ The diagnosis must be confirmed at the time of the screening visit
4. MMSE-2 score of 4-15 inclusive (applies to Screening Visit only)
5. Patients must be able to perform at least one item on the SIB and may not have a SIB score >93 at screening
6. Neuroimaging computerized tomography (CT) or Magnetic Resonance Imaging (MRI) within the last 24 months consistent with a diagnosis of probable AD without any other clinically significant co-morbid pathologies. If there has been a significant change in the subject's clinical status since the last imaging study that is not consistent with progression of the subject's AD, an imaging study should be performed to confirm eligibility
7. Reliable caregiver(s) or informant(s) who attends the subject at least an average of 3 hours or more per day for 3 or more days per week and who will agree to accompany the subject to the clinic visits and reliably complete the caregiver questions
8. Adequate vision and motor function to comply with testing
9. If taking an approved cholinesterase inhibitor for treatment of Alzheimer's disease, must be on a stable dose for at least 3 months prior to entry into study and the dose must not change during the study unless a change is required due to an adverse effect of the prescribed medication or a clinically significant change in the patient's status
10. Subjects who are memantine naïve or have been off memantine for at least 30 days prior to initial treatment with study drug
11. Subjects on neuroleptic medications must be on a stable dose for ≥ 4 weeks (dose adjustments will be permitted)
12. Females participating in the study must meet one the following criteria:
 - a. Surgically sterilized (e.g., hysterectomy, bilateral oophorectomy or tubal ligation) for at least 6 months or postmenopausal (postmenopausal females must have no menstrual bleeding for at least 1 year) or

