7.1 Adverse Event of Special Interest - Myalgia

Myalgia has been reported as the dose limiting toxicity across the oncology studies. The incidence of myalgia appears to be dose dependent and cumulative. However, it has been reported in subjects receiving doses as low as $5\mu\text{g}/\text{m}^2$. The myalgia has been investigated in some studies but not all. No increase in muscle enzymes were found in the cases investigated. EMG was abnormal in one subject who received $65\mu\text{g}/\text{m}^2$ and suggested a patchy myositis. An MRI done in another subject was normal.

For all cases of myalgia despite the severity, a narrative will be created documenting onset, severity, treatment and outcome. Muscle enzymes, CPK, will be collected for all cases and compared to baseline values. Additional investigations are at the discretion of the investigator.

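### Myalgia, the adverse event of special interest, has no active ascertainment in subjects with MMSE-2 4-15, so a low count could not be read as evidence of absence

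*Protocol*

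**What the plan says.** Protocol section 7.1 singles out myalgia as the event of special interest and gives the reason: "Myalgia has been reported as the dose limiting toxicity across the oncology studies". It describes the incidence as appearing dose dependent and cumulative.

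Detection is governed by the general rule in section 7.0: "All adverse events spontaneously reported by the subject and/or caregiver in response to an open question or revealed by observation will be recorded". The special provisions begin once a case is known:

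- Section 7.1: "For all cases of myalgia despite the severity, a narrative will be created documenting onset, severity, treatment and outcome".
- Section 6.1.1.1: "A serum creatine phosphokinase (CPK) will be done at screening and in the event of myalgia".
- Section 7.6.1 requires immediate notice to the Medical Monitor.

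Between the first and last dose, Table 1 and section 6.2.7 schedule one physical exam, at Week 7: "Abbreviated Physical exam". Section 6.1.1.2 defines it: "An abbreviated PE will include but is not limited to the following" general appearance, weight, respiratory system, cardiovascular system and abdomen. The complete exam adds musculoskeletal/neurologic.

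Inclusion criterion 4 admits MMSE-2 scores of 4 to 15. Criterion 7 asks for a caregiver who "attends the subject at least an average of 3 hours or more per day for 3 or more days per week".

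SAP section 8.3.1 summarizes TEAEs by system organ class and preferred term. It plans no summary specific to myalgia or to events of special interest.

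**The concern.** Muscle pain is a symptom that someone has to report. Many of these subjects may be unable to volunteer it, and the caregiver who speaks for them may see them for only part of the week. The protocol names the event, says why it matters, and specifies carefully what to do with a known case, but it does nothing extra to find one.

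Safety and tolerability are part of the primary objective (Protocol section 3.0). The sponsor already treats low myalgia counts as informative: the dose rationale (section 4.1) says the oncology pattern was not seen in studies NTRP101-201 and NTRP101-202. If this trial also yields few cases, the reader will not know whether myalgia was rare or went unreported.

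**Working it through.** No figure in the plan decides this point, so the check has two parts: whether any route actively looks for myalgia, and how much incomplete detection could matter.

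**1. Routes by which a case could surface**

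- *Questioning.* Section 7.0 provides an open question to subject and/or caregiver. Neither document contains a scripted myalgia item, checklist or pain scale.
- *Observation.* Also in section 7.0, but unstructured.
- *Laboratory.* After screening, CPK is drawn only when myalgia has been reported, so it cannot flag an unreported case. Routine CPK might not help either, since section 7.1 says of earlier cases: "No increase in muscle enzymes were found in the cases investigated".
- *Examination.* The Week 7 exam (Day 49, before Dose 5) has a minimum list without the muscles. Other systems are examined to explore an event already reported. The Week 13 exam (Day 91) is not marked abbreviated, so it should include the musculoskeletal system. It falls 91 − 77 = 14 days after Dose 7.
- *Medication review.* Done at every visit (section 6.3), so a new analgesic could lead to a query.
- *Caregiver contact.* The minimum is 3 hours × 3 days = 9 hours a week.

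None of these asks about myalgia directly.

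**2. Rates the documents can anchor**

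Section 2.1.4 gives numbers and percentages with treatment-related TEAEs in study 202. These imply the arm sizes: 8/0.167 ≈ 48 on placebo, 17/0.370 ≈ 46 on 20 µg and 24/0.511 ≈ 47 on 40 µg. The sum is 141, matching the safety set in section 2.1.3. Five subjects had myalgia, four of them on 40 µg. The arm of the fifth is not stated.

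- 40 µg: 4/47 = 8.5%.
- 20 µg: at most 1/46 = 2.2%, if the fifth case was there.
- Placebo and 20 µg together: 1/94 = 1.1%.
- Oncology monotherapy, discontinuation for myalgia (section 2.0): 28/584 = 4.8%, taking the approximately 584 monotherapy subjects as denominator.

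**3. Effect of incomplete detection**

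Let p be the true risk on bryostatin and s the share of cases detected. With 50 subjects (100 randomized 1:1), the expected number seen is 50ps, and P(at least one) = 1 − (1 − ps)^50. Both p and s are assumptions; the documents give neither for this trial.

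| True risk p | Expected cases, s = 1 | Expected cases, s = 0.5 | P(≥1), s = 1 | P(≥1), s = 0.5 |
|---|---|---|---|---|
| 2.2% (1/46) | 1.09 | 0.54 | 67% | 42% |
| 5% | 2.50 | 1.25 | 92% | 72% |
| 8.5% (4/47) | 4.26 | 2.13 | 99% | 89% |

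For example, at 5%: 1 − 0.95^50 = 0.923 and 1 − 0.975^50 = 0.718.

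**4. Effect on the comparison**

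If the same share s is detected in both blinded arms, the ratio of expected rates is unchanged: s·p₁/(s·p₀) = p₁/p₀. The absolute rates and the risk difference, s(p₁ − p₀), shrink by the factor s.

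**The case against.** The best defence is that open-question collection is a legitimate design choice and safeguards surround it. The caregiver is named in the same sentence as the subject, must be reliable and must attend visits; 9 hours a week is a floor. Adverse events and medications are reviewed at every visit, and section 6.3.2 deals specifically with medication for myalgia. The abbreviated exam list is a minimum. The Week 13 exam follows all seven doses, which matters if myalgia is cumulative, and its 14-day gap is no longer than the gap between Dose 4 and the Week 7 exam (49 − 35 = 14). Study 202, in a similar population, recorded five cases that were mostly mild, so mild cases can be found.

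Rarity also explains much of any low count. At 2.2%, one case or none in 50 has probability 1 − 0.297 = 70% with full detection and 1 − 0.103 = 90% with half.

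Most of this stands, and it rules out two stronger readings. A reader might infer that myalgia *will* be under-counted. The documents give no detection rate, so only *may be* is supported. A reader might also infer that the trial would declare the regimen free of myalgia. No section plans that conclusion; section 9.3 makes safety descriptive, without hypothesis tests.

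The safeguards do not supply active ascertainment. Each depends on someone volunteering the symptom, noticing it, or starting a drug for it, or on an exam at which an earlier transient event may be gone. The five cases in study 202 show that some are found, but not what share.

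**Conclusion.** The point holds as a gap in ascertainment. The event of special interest is collected passively, in subjects whose self-report may be unreliable, and everything specific to it starts after detection. A low count in this trial could not be taken as evidence that myalgia is absent.

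The size is illustrative. Halving detection would lower the chance of seeing any case among 50 bryostatin subjects by about 25 percentage points at a true risk of 2.2%, 20 at 5% and 10 at 8.5%. These rest on assumed true risks and an assumed detection share. The 2.2% also assumes that the fifth case in study 202 was on 20 µg, and that figure could itself be too low if study 202 missed cases. The primary efficacy analysis is not affected. The change is worth making because it is cheap and serves a stated primary objective.

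**What to change.** - **Protocol section 7.1 and Table 1.** At each visit after Dose 1, and after the open adverse event question, ask subject and caregiver one scripted yes/no question on muscle pain or tenderness. Record the answer in its own eCRF field. The PI judges whether a yes is a myalgia adverse event; the existing provisions of sections 7.1 and 7.6.1 apply only if it is.
- **Protocol section 6.1.1.2.** Add musculoskeletal to the minimum list for the Week 7 abbreviated exam. This is a small supplement, since an exam adds less than a question for a subjective symptom.
- **SAP section 8.3.1.** Add a table of myalgia by arm, showing prompted-only cases separately from spontaneously reported TEAEs.

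The cost is one question per visit, one eCRF field, one exam line and one table, with no new staff. Prompting will bring more non-specific background reports in both arms; the placebo arm and the separate table handle most of that. Some comparability with study 202 may be lost, because the documents do not say how its events were elicited and a prompt at one visit may influence spontaneous reports at the next.
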